14.2 Serious Adverse Event

SAE refers to any untoward medical occurrence in a clinical trial that results in death or serious deterioration of health status, including life-threatening conditions or damage, permanent defect of body structure or body function, events requiring inpatient hospitalization or prolongation of existing hospitalization, those requiring medical or surgical intervention to avoid permanent defect of body structure or body function; and those resulting in fetal distress, fetal death or congenital anomaly/birth defect, etc.

A planned hospitalization and/or medical intervention for pre-existing conditions, or a procedure required by the protocol, without serious deterioration in health, is not considered to be a serious adverse event.

14.3 Device Complaints

A product complaint is defined as any written, electronic or oral communication that alleges deficiencies related to the identity, labelling, quality, durability, reliability, safety, efficacy, or performance of a device after it is released for distribution. In the event of any device complaint, the study site must inform the monitor and track and report it according to the process stipulated by the Sponsor. The study site must inform the study monitor of all device complaints of the study groups and control group. The monitor will track and report device complaints according to the method and time limit stipulated by the Sponsor and China's laws and regulations and return related products to the quality department of ██████████ upon the request of the Sponsor.

14.4 Device Defects

Device defects refer to unreasonable risks of medical device existing during the clinical trial

under normal use, which may endanger human health and life safety, such as labeling error, quality problem, malfunctioning, etc.

In the event of any device defect that may lead to SAE, the Sponsor should report it to the Food and Drug Administration Department and Health Planning Department at the same level within 5 working days after the awareness of the defect. The Sponsor will notify other clinical trial institutions and investigators participating in the trial and notify the EC of the clinical trial institution involved in a timely manner via its medical device clinical trial management department. The investigator should record all AEs occurring and device deficiencies found in the process of clinical trial, work with the Sponsor to analyze the causes of the events, generate the written analysis report, present the comments on the continuation, discontinuation or termination of the trial, and report to the Ethics Committee by the administrative department for clinical trial of medical device of clinical trial institution for review.

14.5 Reporting Procedure and Contact Person Information

The investigator should ensure sufficient treatment is given for any AE experienced by a subject, including clinically significant laboratory test values related to this study.

Once a subject is randomized, his/her AE should be followed up, until they are resolved or stabilized and the clinical outcome has been determined, or until his/her last follow-up visit (the earliest one shall prevail). If the investigator considers the AE is related to the study product, the subject must be followed up until the event is resolved and stabilized.

The investigator must report the AE to the Sponsor via e-CRF within 2 weeks after its awareness. The Investigator should record the nature, severity, treatment and outcome of AE and determine whether the AE is related to the study device, medication, or surgical procedure defined in the study protocol or not.

All the SAEs must be followed up until they are resolved (with or without sequela). When the event is not resolved or stable at the end of study, the medical monitor in this clinical study will decide whether it is necessary to collect the further follow-up information. The Investigator should send a report to regulatory agencies at different levels, EC and the Sponsor within 24 hours after the awareness of a SAE.

The Investigator must report any SAEs and any device defects possibly leading to SAE that occur during the study to the Sponsor and related regulatory department required by laws and regulation within 24 hours after the awareness of the event or defect; and provide further information upon the sponsor's request.

For any SAE and device defect that may lead to SAE, the Investigator should report it to the regulatory authorities, EC and the Sponsor within the time limit defined by the Sponsor. According to the requirements of No.25 Decree, the Sponsor should report the SAE or defect to the Food and Drug Administration Department and Competent Department of Health and Family Planning at the same level within 5 working days after its awareness. – The Sponsor will notify other clinical trial institutions and investigators participating in the trial and notify the EC of the clinical trial institution involved in a timely manner via its medical device clinical trial management department.

The investigator should record all AEs occurring and device deficiencies found in the process of clinical trial, work with the Sponsor to analyze the causes of the events, generate the written analysis report, present the comments on the continuation, discontinuation or termination of the trial, and report to the Ethics Committee by the administrative department for clinical trial of medical device of clinical trial institution for review. Once a device complaint is found, the site should inform the Sponsor as soon as possible, and report the device related information on the relevant CRF.

In the event of a device failure, the study site must notify the clinical monitor as soon as possible.

The monitor should coordinate related departments and return the product to the quality department of ██████ according to the Sponsor's schedule.

The contact persons for AE and device defect reporting are as follows:

AE: ██████.com ██████.com

Device Complaints: ██████.com

15. Deviation From Clinical Trial Protocol And Regulations For Clinical Trial Protocol Amendment

The study protocol deviations are defined as the circumstances that fail to comply with the requirements of clinical trial protocol intentionally or unintentionally.

All protocol deviations should be reported as protocol deviations to the Sponsor via protocol deviation form and monitoring visit report. The reporting should include the date and reason for protocol deviations. The Investigator should also report the protocol deviations to hospital's medical device clinical trial management department, and report to EC via them, in accordance with the procedures and regulations and the requirements of the hospital.

If a protocol amendment occurs, the Sponsor or designated person should submit a summary of changes of the study protocol to the Investigator, regulatory authority, and the Ethics Committee, etc. according to the relevant laws and regulations. All major amendments must be approved by the Ethics Committee and regulatory authority (if needed) prior to implementing any changes to study procedures.

An amendment is regarded substantial when they are likely to have a significant impact on:

- The safety or physical or mental integrity of the subjects;
- Scientific value of trial;
- Conduct or management of the trial;
- Quality or safety of investigational medical device specified in the trial.

16. Direct Access to Source Data and Document

The source data is defined as all information in the subject's original medical record and its approved copy regarding the clinical findings, observations and other activities in the clinical trial, which can be used for reproduction and evaluation of clinical trial. The source documents are documents on which the source data is recorded, including printed, paper or electronic documents.

The subject's medical record and other study related documents (source documents) must be maintained and retained by the Investigator. The Investigator should allow the monitors and auditors/inspectors to review all relevant subject records, including but not limited to the following information:

- Medical/physical condition of the study subject that meets the inclusion criteria prior to participating this study;
- Medical record documenting the informed consent process;
- Operational description of use and implantation of the study product;
- All inspection results and follow-up;
- Examined printed output file or report (for example, X-ray film) that is dated and signed;
- Imaging or video data of wound healing status;
- Description of AE and follow-up of AE (description of event, severity, date of occurrence, duration, correlation with the study device, study procedure, outcome, and treatment of the AE, concomitant medications when the AE occurs);

- Description of product complaint;
- Study subject's status at the end of the study or withdrawn from the study.

Subject's medical documents including the medical record, examination reports, films, imaging records, etc. The Sponsor expects that, appropriate study coordinator and/or investigator, appropriate original source documents and an appropriate environment will be available during the monitoring visit for review of study-related documents. All the inconsistencies between the e-CRF and source documents must be marked and resolved via discussion with the investigator or designated person.

17. Finances and Insurance

See relevant study contract and insurance document.

18. Contents Should Be Covered by Clinical Study Report

According to regulatory requirements, the clinical study report will contain the following contents:

The clinical trial report should be consistent with the clinical trial protocol, mainly containing:

- (1) General information;
- (2) Synopsis;
- (3) Introduction;
- (4) Objective of clinical trial;
- (5) Method of clinical trial;
- (6) Contents of clinical trial;
- (7) General clinical information;
- (8) Investigational medical devices and control medical devices or control diagnosis and treatment method;
- (9) Statistical analysis method(s) and evaluation method(s) adopted;
- (10) Clinical evaluation criteria;
- (11) Organizational structure of clinical trial;
- (12) Description of ethics profile;
- (13) Clinical trial results;
- (14) Adverse events found during the clinical trial and corresponding treatment;
- (15) Analysis and discussion of clinical trial results, especially indications, scope of application, contraindications and precautions;
- (16) Clinical trial conclusion;
- (17) Existing problems and suggestions for improvement;
- (18) List of study personnel;
- (19) Other situations requiring explanation;
- (20) Clinical trial summary of each study site.

19. Confidentiality Principle

The personal data of the subject participating in the trial is confidential; however, the EC, CFDA, Competent Department of Health and Family Planning, or the Sponsor and its authorized representative may review the personal data of the subject participating in the trial for the purpose of their work according to the local established procedure.

Subject confidentiality will be maintained throughout the clinical study in a way that ensures the information can always be tracked back to the source data. For this purpose, a unique subject identification code (site number and subject number) will be used that allows identification of all data reported for each subject. As long as the data is kept strictly confidential and that the privacy of the subject is ensured to be protected, the data related to this study may be available

to third parties (for example, under the audit of regulatory authority).

20. Agreement on the Publication of Trial Results

At the conclusion of the study, a multicenter manuscript will be prepared for publication in a reputable scientific journal. The publication of the principal results from any single-site experience within the study is not allowed until the preparation and publication of the multicenter results. Exceptions to this rule require the prior approval of the Sponsor. The analysis of other pre-specified and non-pre-specified endpoints will be performed by Data Management. Such secondary analyses, as well as other proposed investigations, will require the approval of the Sponsor. For purposes of timely abstract presentation and publication, secondary publications will be delegated to the appropriate principal authors, and final analyses and manuscript review for all multi-center data will require the approval of the Sponsor.

21. Responsibilities That Each Party Should Bear

21.1 Sponsor Responsibility

- 1) The Sponsor is responsible for the initiation, application, organization and monitoring of clinical trial.
- 2) The Sponsor is responsible for the organization to establish and modify the investigator brochure, clinical trial protocol, informed consent form, Case Report Form, relevant standard operating procedure and other relevant documents, carry out the training required for the clinical trial, and provide these documents to the investigators before the study starts.
- 3) The Sponsor should select the qualified trial institution and investigators.
- 4) The Sponsor should sign a written agreement with the clinical trial institution and the Investigator regarding the clinical trial.
- 5) The Sponsor should provide qualified study product according to the regulatory requirements. The Sponsor should be responsible for the safety of investigational medical product in the clinical trial. The AE, SAE, and the product complaint that may cause an SAE should be collected and reported in accordance with the provisions.
- 6) The Sponsor should inform the regulatory authority at every level when the Sponsor decides to suspend or terminate the clinical trial or at the end of the study.
- 7) The Sponsor should ensure the Investigator conducts the study strictly in compliance with the clinical trial protocol, corrects the protocol deviations in a timely way, and reserves the rights to report, to the regulatory authority, any of issues related to this.
- 8) The Sponsor should bear the treatment cost and relevant economic compensation for the clinical trial-related injury or death of subjects, with the exception of damages due to the fault of medical institution and medical staff in the diagnosis and treatment.
- 9) The Sponsor should select qualified monitors for monitoring and organizing any inspections, as appropriate.

21.2 Responsibilities of Clinical Trial Institution and Investigator

- 1) The clinical trial institution should evaluate the relevant resources according to the features of investigational medical product prior to the clinical trial, so as to decide whether to participate in this clinical trial.
- 2) The clinical trial institution should properly keep the records and essential documents of clinical trial according to the agreement with the Sponsor.
- 3) Ensure the Investigators who are responsible for the clinical trial have the qualification in accordance with the requirements of related laws and regulations.
- 4) The administrative department for clinical trial of medical product of clinical trial institution should cooperate with the Sponsor to apply to the Ethics Committee and submit the relevant documents prior to the clinical trial according to requirements.

- 5) The investigator should ensure that the relevant workers participating in the trial have the enough resources and proper training, and keep the training related documents.
- 6) The Investigator should ensure to use the investigational medical product only for the subjects of this clinical trial, and may not charge any fee.
- 7) The Investigator should strictly follow the clinical trial protocol, with the exception of emergency circumstances when the subject faces the direct risk and needs immediate clinical measures, which can be reported later in a written form.
- 8) The Investigator is responsible for recruiting the subjects, communicating with the subject or its legal representative before signing the informed consent.
- 9) The Investigator should protect the rights, safety and health of the subjects.
- 10) In case of a SAE occurring in the clinical trial, the Investigator should protect the safety of the subjects and timely report the event to the regulatory authority.
- 11) The investigator should record all AEs occurring and device deficiencies found in the process of clinical trial, work with the Sponsor to analyze the causes of the events, generate the written analysis report, present the comments on the continuation, discontinuation or termination of the trial, and report to the Ethics Committee by the administrative department for clinical trial of medical device of clinical trial institution for review.
- 12) The Investigator should ensure that the clinical trial data is accurately, completely, clearly and timely recorded in the Case Report Form.
- 13) The clinical trial institution and investigator should make sure that the data, documents and records generated in the clinical trial are timely, true, accurate, clear, and attributable.
- 14) The clinical trial institution and Investigator should accept and cooperate with the monitoring and audit of the Sponsor, the supervision of the Ethics Committee, and the inspection of the Food and Drug Administration, competent department of health and family planning, etc., and provide all required records related to the trial.
- 15) If the clinical trial needs to be suspended or terminated, the subjects should be informed accordingly, and it should be ensured that the subjects receive the proper care and follow-up. The clinical trial institution and Investigator should also report this in accordance with the regulations and provide a detailed written explanation. The relevant report should be submitted to the local Food and Drug Administration at the provincial, autonomous regional and municipal level, if necessary.
- 16) The clinical trial institution and investigator reserve the rights to report to the regulatory authority at every level when the Sponsor violates relevant laws and regulations.
- 17) The Investigator should complete all records and reports at the end of clinical trial. The Investigator should also ensure that the received investigational medical products are properly handled and recorded according to the requirements.

Annex 2: List of Specifications and Models

[Investigational Product]:

[REDACTED]

Unidirectional barbed model	SXPP1B450	SXPP1B416	SXPP1B423	SXPP1B428
SXPP1B201	SXPP1B407	SXPP1B417	SXPP1B424	SXPP1B432
SXPP1B203	SXPP1B408	SXPP1B418	SXPP1B425	SXPP1B433
SXPP1B204	SXPP1B202	SXPP1B419	SXPP1B111	SXPP1B434
SXPP1B205	SXPP1B451	SXPP1B103	SXPP1B112	SXPP1B453
SXPP1B429	SXPP1B452	SXPP1B104	SXPP1B113	SXPP1B454
SXPP1B430	SXPP1B409	SXPP1B105	SXPP1B114	SXPP1B455
SXPP1B431	SXPP1B410	SXPP1B106	SXPP1B115	SXPP1B456
SXPP1B401	SXPP1B411	SXPP1B420	SXPP1B116	SXPP1B457
SXPP1B402	SXPP1B412	SXPP1B421	SXPP1B117	SXPP1B458
SXPP1B403	SXPP1B413	SXPP1B107	SXPP1B118	
SXPP1B404	SXPP1B414	SXPP1B108	SXPP1B119	
SXPP1B405	SXPP1B101	SXPP1B109	SXPP1B120	
SXPP1B406	SXPP1B102	SXPP1B110	SXPP1B426	
	SXPP1B415	SXPP1B422	SXPP1B427	

Bidirectional barbed model	SXPP2B416	SXPP2B413	SXPP2B412	SXPP2B432
SXPP2B422	SXPP2B200	SXPP2B414	SXPP2B409	SXPP2B433
SXPP2B423	SXPP2B201	SXPP2B440	SXPP2B410	SXPP2B401
SXPP2B417	SXPP2B202	SXPP2B441	SXPP2B411	SXPP2B402
SXPP2B419	SXPP2B203	SXPP2B442	SXPP2B427	SXPP2B403
SXPP2B418	SXPP2B426	SXPP2B443	SXPP2B428	SXPP2B434
SXPP2B420	SXPP2B425	SXPP2B406	SXPP2B429	SXPP2B400
SXPP2B415	SXPP2B424	SXPP2B407	SXPP2B430	SXPP2B405
	SXPP2B404	SXPP2B408	SXPP2B431	SXPP2B435

[REDACTED]

Unidirectional barbed model	SXMP1B416	SXMP1B429	SXMP1B110	SXMP1B114
SXMP1B408	SXMP1B417	SXMP1B101	SXMP1B111	SXMP1B115
SXMP1B409	SXMP1B419	SXMP1B102	SXMP1B113	SXMP1B116
SXMP1B410	SXMP1B420	SXMP1B103	SXMP1B430	SXMP1B117
SXMP1B411	SXMP1B421	SXMP1B104	SXMP1B431	SXMP1B118
SXMP1B412	SXMP1B424	SXMP1B105	SXMP1B432	SXMP1B119
SXMP1B413	SXMP1B425	SXMP1B106	SXMP1B433	SXMP1B120
SXMP1B414	SXMP1B426	SXMP1B107	SXMP1B434	SXMP1B437
SXMP1B415	SXMP1B427	SXMP1B108	SXMP1B435	SXMP1B438
	SXMP1B428	SXMP1B109	SXMP1B436	SXMP1B439

Bidirectional barbed model
SXMP2B405
SXMP2B407
SXMP2B409
SXMP2B151
SXMP2B404
SXMP2B406
SXMP2B408
SXMP2B152
SXMP2B150
SXMP2B410
SXMP2B424
SXMP2B425
SXMP2B426
SXMP2B413
SXMP2B411
SXMP2B412
SXMP2B414
SXMP2B403
SXMP2B402
SXMP2B415
SXMP2B416
SXMP2B417
SXMP2B418
SXMP2B419
SXMP2B420
SXMP2B400
SXMP2B401
SXMP2B421
SXMP2B422
SXMP2B423

██████████ LLC, ██████████

ESC-201702

[PROTOCOL VERISON AND DATE] V2.0/2019-09-30

[Control Product]:

【██████████】: ██████████

【██████████】: ██████████

【██████████】: ██████████

Annex 3: Modified Hollander Wound Evaluation Scale

Modified Hollander Cosmesis Score

Parameter	Definition	Assessment	Yes	No
Step off borders	Edges not on same plane	As you run finger over the healed wound, is there a step or the edges?	1	0
Contour irregularities	Wrinkled skin near wound	Is the skin near the wound wrinkled or puckered?	1	0
Incision margin separation	Gap between sides	Is the gap between the wound edges at the widest point (i.e., scar width) >2 mm?	1	0
Edge inversion	Wound not properly everted	Either of the wound edges invert (sink or cut) into the wound?	1	0
Excessive inflammation	Redness, swelling/oedema discharge from wound	Is there evidence of swelling, redness or discharge from the wound?	1	0
Overall Appearance			Poor=1	Good=0

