7.1.6 Efficacy Evaluation Method

1) Description of efficacy parameters

The primary efficacy endpoint is defined as the proportion of subjects achieving Grade A healing (success) of surgical incision in each group.

According to clinical routine practice, wound healing status should be assessed during removal of stitches of incision and generally, stitches at the incision of head, face and neck are taken out on Day 4-5 post-surgery; however, if energy devices are used (e.g. electrotome), the removal of stitches should be delayed by 1-2 days. In this study, all the skin layers can be performed with intradermal continuous suture using absorbable sutures, thus it is unnecessary to take out stitches at the incision. Therefore, the time of wound healing assessment in this study is set as Day 5-7 post-surgery.

Wound healing status is classified into three grades:

- Grade A healing: Good healing with no adverse reaction;
- Grade B healing: Inflammatory reaction(s) at the healing, such as red swelling, induration, hematoma, effusion, etc., but without suppuration;
- Grade C healing: Suppuration of incision, requiring incision and drainage and other treatments.

Secondary Efficacy Endpoints include:

1. Incision suturing time, defined as the time required from the first needle insertion for stitching ribbon muscles to the completion of intradermal suture (min);
2. Modified Hollander Wound Evaluation Scale (see Annex 3), assessed by Imaging Center evaluators using pictures, including: a picture of complete neck anterior view containing full length of the incision, a picture taken parallel to the incision plane, a picture taken at a 45° angle to the incision plane, and incision lateral view pictures of both sides (one for each);
3. Postoperative incision pain score (VAS scale, see Annex 4-1);
4. Health related quality of life scale (EQ-5D-5L): Subjects are required to select the most appropriate levels in 5 aspects to determine their health status (see Annex 5):
 - Motility
 - Self care
 - Daily activities
 - Pain/discomfort
 - Anxiety/depression

2) Selection of method and time to evaluate, record and analyze the efficacy parameters

The primary efficacy endpoint (wound healing grade) will be assessed by independent, blinded Imaging Center according to the picture (a picture of complete neck anterior view, containing full length of the incision) on Day 5-7 post-surgery and documented in the e-CRF.

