- g. Assessed by Central Imaging evaluators using imaging data provided by study sites.
- h. Including incisional wound separation or wound dehiscence requiring intervention, target incisional wound healing delay, etc.

- i. For subjects who are randomized but without any of study sutures used for incision closure, this visit is conducted as early as possible. For subjects who withdraw ICF, this visit is conducted as early as possible with subjects' permission. Telephone visit is acceptable.

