### **13.2.2. MODIFIED HOLLANDER WOUND EVALUATION SCALE**

Assessed by Imaging Center evaluators using pictures, including: a picture of complete neck anterior view containing full length of the incision, a picture taken parallel to the incision plane, a picture taken at a 45° angle to the incision plane, and incision lateral view pictures of both sides (one for each);

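### One of the six modified Hollander items is worded as a finger test but is read from pictures, and a second needs a size reference that the picture specification does not require

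*Protocol*

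**What the plan says.** Annex 3 lists six yes/no items, each worth 0 or 1: step-off borders, contour irregularities, margin separation, edge inversion, excessive inflammation and an overall rating. Each of the first five has a definition and a separate assessment prompt.

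- Step-off borders: the definition is "Edges not on same plane"; the prompt is "As you run finger over the healed wound, is there a step or the edges".
- Margin separation: the prompt is "Is the gap between the wound edges at the widest point (i.e., scar width) >2 mm".

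The plan is consistent about who scores the scale and from what. Protocol 7.1.6 has "Modified Hollander Wound Evaluation Scale (see Annex 3), assessed by Imaging Center evaluators using pictures". Footnote g to the schedule in 7.2.1 says "Assessed by Central Imaging evaluators using imaging data provided by study sites". SAP 13.2.2 repeats it: "Assessed by Imaging Center evaluators using pictures, including: a picture of complete neck anterior view". Section 7.1.6 also names the imaging evaluators' records as the source for this scale. No bedside score by the investigator is described.

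Footnote f of 7.2.1 and the Visit 5 list in 7.2.3 ask for five pictures: one frontal, one parallel to the incision plane, one at 45° and one lateral view from each side. Neither place mentions a ruler, scale marker or camera distance.

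**The concern.** A remote reader cannot run a finger over a wound. Neither document adapts that prompt for photographs, so each reader must decide what to do with it, and readers may decide differently. The margin item has a related difficulty: judging an absolute width against 2 mm requires knowing the scale of the picture.

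This scale is the only endpoint devoted to cosmesis. Protocol 4.1 gives the appearance of the neck incision as a growing concern of patients, and 4.3 says the trial is meant to show that barbs do no harm to safety or efficacy. Step-off and margin gap both bear on how well the suture brings the edges together. If these items are scored inconsistently, the added noise tends to blur any difference between arms, and in this trial a blurred difference reads as reassurance. Blinding the readers protects against biased scoring, but it does not make an item observable.

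**Working it through.** The plan states no figure on this point, so there is none to reproduce. The check compares each Annex 3 item with what a central reader has at Visit 5.

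| Annex 3 item | What the prompt needs | Available from the five specified pictures? |
|---|---|---|
| Step-off borders | touch | No, as the prompt is worded; the definition can be judged by eye |
| Contour irregularities | sight | Yes |
| Margin separation | width against 2 mm | Only with a size reference, which is neither required nor excluded |
| Edge inversion | sight | Yes |
| Excessive inflammation | sight | Yes |
| Overall rating | sight | Yes |

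Count of items:

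- In outright conflict with picture-only scoring: 1 of 6; 1/6 = 17%.
- Affected if the pictures carry no size reference: 2 of 6; 2/6 = 33%.

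Three further readings of the text set the limits of the point.

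1. **Scoring rule.** Neither Annex 3 nor SAP 13.2.2 says that the items are added up. The percentages above are therefore shares of items, not shares of a defined total score.
2. **Unscorable items.** Annex 3 offers only yes or no. Protocol 8.7 and SAP 7.1 say that available data are used and nothing is imputed. No passage says what a reader records when an item cannot be judged.
3. **Use of the result.** Protocol 8.1 and SAP 13.2.5 summarise secondary efficacy endpoints descriptively on the FAS, without inferential statistics. Nothing in the primary hypothesis, the Holm procedure or the sample size uses this scale.

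**The case against.** The strongest reply is that the step-off item is defined visually and only its prompt is tactile. The parallel, 45° and lateral views could well show a difference in height between the edges, so a sensible reader can score the item. That stands in part: it shows the item can be rescued. It does not remove the conflict, because the prompt is the instruction to the assessor and it calls for touch.

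A second reply is that the picture lists describe views, not photographic technique, so silence about a ruler does not mean there is none. That stands. A reader might infer that the pictures are unscaled and that two items are therefore unscorable. The documents support only that a size reference is not required.

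A reader might also infer that unscorable items will be set to 0, the best score, so that a 0 to 6 scale shrinks to 0 to 4 and every arm looks good. The documents give no default of 0 and no total score. Under the rule against imputation, a blank item would more naturally be missing.

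Nor can the effect be put at all 501 planned subjects. Protocol 8.4 expects 10% dropout, and the withdrawal visit for subjects in whom no study suture was used includes no pictures.

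Finally, the readers are blinded and the endpoint is descriptive, so no mechanism favouring one arm is shown. Other Annex 3 items, and the recording of wound separation and delayed healing at Visits 4 and 5, also cover part of the same ground. This limits the weight of the point but does not answer it.

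**Conclusion.** The point holds in a narrow form. One of six items (17%) cannot be assessed as its prompt is worded, because the prompt requires touch and the readers have only pictures. A second item (bringing the count to 2 of 6, or 33%) rests on a size reference that the plan does not require; whether it can be scored depends on site photography that the documents leave open.

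The consequence is reduced validity of a descriptive secondary endpoint. The size of any effect on the reported scores cannot be derived from the documents, since they give neither a scoring rule nor a rule for items that cannot be judged. The primary comparison is unaffected. The point is worth acting on because the conflict is explicit and the correction is cheap.

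**What to change.** 1. **Annex 3.** Reword the step-off prompt for photographs so that it asks what the definition already says, judged from the parallel, 45° and lateral views. All six items then stay with the blinded readers.
2. **Protocol 7.2.1 footnote f and 7.2.3 Visit 5.** Require a ruler or scale sticker beside the incision in the frontal Visit 5 picture, so that the 2 mm item can be measured.
3. **SAP 13.2.2.** Report the six items individually by arm, with a not-assessable category that is counted separately and never scored as 0.

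The cost is one disposable marker per subject and a small change to the reading form. Pictures already taken without a marker would be reported as not assessable for the 2 mm item.

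Having the site score step-off by touch at Visit 5 is the other possible route. It is less attractive because the suturing investigator cannot be blinded (Protocol 7.1.3) and no blinded site assessor is described, so one item would lose the protection the plan gives to the scale.
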